Guided by the model and our findings in GWI patients, we propose to examine the effects of transcranial direct-current stimulation (tDCS) on preSMA to improve semantic retrieval processes that support word finding/retrieval. TDCS appears to be a viable alternative or adjunct treatment option for cognitive dysfunction.²⁰ The application of tDCS has resulted in improved language abilities, including verbal fluency^{21, 22}, in aphasic patients and healthy controls after delivery of stimulation to frontal and temporal lobe regions.²³. TDCS has been has been shown to lead to relatively localized metabolic change²⁴ and change in neuronal resting membrane potentials mediated by changes in sodium and calcium dependent channel function.²⁵ TDCS has been proposed to increase the neuronal firing rate leading to changes in long-term potentiation and depression²⁰ and purportedly leads to long-term enhancement of signal transmission between neurons that can strengthen neuronal connections, and subsequently strengthening the retrieval circuit. Thus, we will use tDCS to

improve function in a dysfunctional semantic retrieval circuit in order to treat word finding deficits in patients with GWI.

While we plan to stimulate the preSMA, we predict that the stimulation will affect the entire retrieval circuit. Based on our Neural Hybrid Model in which the preSMA mediates comparator/switching processes in word retrieval, applying tDCS at preSMA has the potential to strengthen neuronal connections disrupted by pathology within the preSMA, caudate and thalamus, and to improve the functioning of the retrieval circuit¹⁹. In turn, we predict improvements in verbal fluency, word finding problems, and potentially verbal episodic memory (see Preliminary Studies).

[figure not shown]
Preliminary Studies

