Preliminary Study #3. A group of 25 Gulf War veterans who complained of cognitive difficulties and 23 matched controls, who were deployed but not symptomatic, performed the Semantic Selection Tasks. In the more semantically complex task, the cognitive complaint group had significantly greater false-alarm rates in the complex semantic Go/NoGo task and this was accompanied by ERPs whose NoGo P3 was significantly reduced in amplitude compared to the control group (Figure 7). This inability to inhibit an incorrect retrieval, marked by increased false positive responses and a

decrease in P3 NoGo amplitude, will be used in this proposed study as one marker of a dysfunctional retrieval circuit.³⁷

Preliminary Studies with HD tDCS administration for verbal retrieval deficits: Our group also has experience using electromagnetic modulation therapies to improve cognitive and behavioral function in Post-Traumatic Stress Disorder (DOD W81XWH-09-DMRDP-ARATDA) and with Multiple Sclerosis (MS). Preliminary data from our current study of MS have been collected on participants with relapsing-remitting MS. MS patients and healthy controls have undergone neuropsychological baseline testing and then received ten sessions of high-definition (HD) tDCS delivered to the preSMA region at 1 mA for 20 min each session, as we propose to use in this project (Figure 8). Following completion of the treatment sessions, the patients have shown improvement in verbal fluency (with significant improvement in SORT RT,

t[3]=6.47, p=.003), verbal memory, selection and inhibition (with significant improvement in Go RT, t[3]=4.19, p=.01), and executive function. One of the main contributors to neurological deficits in MS is decreased effectiveness of inter-regional connections due to white matter pathology, but it appears that tDCS-mediated changes in primarily neuronal, as opposed to axonal, activity, has been effective in overcoming the effects of white matter damage. Similarly, while white matter abnormalities have been hypothesized to be an important mediator of the neurological deficits in GWI^{see 38}, we believe that our therapeutic approach, will also be effective in mitigating the deleterious neurological effects of GWI.

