Objective #4: Each subject will undergo a detailed neuropsychological battery to characterize his or her cognitive and behavioral status—including targeted tests that should be affected by improved verbal retrieval, tests of cognitive functions to which the treatment may generalize, and tests consisting of purportedly unrelated functions to account for global, generalized cognitive improvement. They will also undergo pre-treatment EEG (SORT task with EEG, Semantic Selection task with EEG). These will be used as outcome measures for the treatment trial. The two primary outcome measures will be the COWAT and CVLT. Secondary outcome measures will be SORT and Semantic Selection task, performance and ERP for both sets of tasks.

Objective #5: These subjects will then be enrolled in the active treatment aspect of the study. Enrollment of 80 participants is the target for enrollment in the active phase of the treatment trial. Half the subjects will first receive HD tDCS at 1 mA for 20 minutes over the preSMA region for 10 daily sessions (1 session 5 days per week for a 2 week period). The remaining subjects will initially receive sham HD tDCS; after all follow-up evaluations are completed, they will receive the active HD tDCS treatment.

Objective #6: Each subject will receive follow-up neuropsychological and EEG testing at 1 week, 3 months, and 6 months after treatment. This last time point for evaluation extends from our preliminary work showing that later, further improvement in electromodulation treatments can occur at 6 months post-treatment. HD tDCS active treatment subjects enrolled early in the study will be followed longer than 6 months if agreeable to assess length of effect.

Following completion of this clinical trial, we will be able to determine whether HD tDCS is an effective treatment for the verbal retrieval deficits associated with GWI. An HD tDCS cap is a relatively inexpensive piece of equipment that can be re-used many times for multiple patient treatments. These caps are readily available, and the application of the treatment regimen is straightforward to administer. Thus, this treatment can be utilized in any VA medical center or clinic around the nation. In addition, the neuro-psychological tests and ERP/time frequency findings may function as clinical markers for diagnosis and treatment efficacy in subsequent treatment trials to measure treatment response.

SPECIFIC AIMS

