The goal of this proposal is to entrain the verbal retrieval circuit using HD tDCS to target the preSMA in order to improve retrieval in impaired GWI patients, using behavioral and electrophysiological markers to assess outcomes. After identifying GWI patients with retrieval deficits using standard neuropsychological measures, we will address the following aims:

Aim 1. Administer 10 20-minute sessions of either 1 mA high definition tDCS or sham to the preSMA region. Subtypes of Gulf War Illness patients have been shown to have dysfunction that disrupts the above-described retrieval circuit.⁸ Transcranial DCS targeted to the preSMA has been shown in preliminary studies in other diseased populations to result in improved performance in tasks that engage this circuit by purportedly strengthening potentially weak connections within the preSMA-caudate-thalamus circuit for verbal retrieval.

Hypothesis #1:HD tDCS to the preSMA will produce long-term modulation of the basal state of the preSMA-caudate-thalamic-cortical retrieval circuit.

Aim 2. Assess neuropsychological and electrophysiological (ERP) markers of verbal retrieval following tDCS therapy. Long-term modulation of the preSMA-caudate-thalamic-cortical retrieval circuit, via tDCS to the

preSMA region, will alter the neurophysiological properties of the circuit due to modulation of the readiness of the retrieval circuit. This will result in changes in neural markers as follows:

Hypothesis #2*a*:*Neuropsychological measures of verbal retrieval that were impaired at baseline will be improved to expected premorbid levels of functioning for the treated individuals.*

Hypothesis #2*b*: Patients with impairments in making a correct retrieval will exhibit both high false negative errors and false positive errors compared to norms²⁷ and a decreased 750-ms ERP amplitude difference between retrievals and nonretrievals on the SORT task. *We hypothesize that after HD tDCS treatment, these patients will improve performance and/or have an increase in amplitude difference in the ERP between retrievals.*

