Electrodes. tDCS is delivered with Sintered Ag/AgCl disc electrodes using customized high-definition electrode with 8-mm diameter resulting in a ~85 \pm 5 mm². The electrode were then filled with > 3 mL of conductive Gel into which the Ag/AgCl disc electrode was immersed. The cotton swab was used to adjust the gel and hair until the electrode resistance was less than 10 k Ω prior to stimulation. The anode was placed over Fz according to the International 10-20 EEG system, corresponding to the approximate location of the pre-SMA. Four return cathodal electrodes were placed approximately 5 cm radially from Fz, corresponding to locations FPz, F7, F8 and Cz (see Figure 8). The preparation procedure consisted of exposing the scalp by separating the hair underlying each electrode and adding approximately 1.5 mL of highly conductive gel. Contact quality and impedance levels were verified for each electrode before each stimulation session began.

Stimulation. Electrical stimulation is performed using a constant voltage Cortical Stimulator (Model D185, Digitimer Ltd, UK, maximal output 1000 V/1.5 A) with single square-wave 50-µs pulses (0.1 A/µs rise time). The adaptor measured resistance prior to stimulation, and divide current during stimulation. HD tDCS will be delivered in the active condition for 20 minutes of 1 milliamp high definition tDCS per session and administered for 10 total sessions on separate days (10 sessions over 10-14 days). This provides focal delivery of current maximally at the preSMA. There is no sensation associated with stimulation at this level, so that the sham condition will consist of placing the HD tDCS cap in place for the 10 sessions of 20 minutes each, but without delivering electrical stimulation. After each session, patients will be administered a standard post-treatment symptom questionnaire (e.g., assessing for skin irritation, fatigue).⁶⁴

E. Potential Problems

1. There is the possibility that the HD tDCS will affect regions other than the preSMA. This will be assessed by reviewing changes in neuropsychological test measures.

2. There is also the possibility that stimulation will be ineffective because the target tissues have been too badly damaged. We will monitor for response patterns consistent with ineffective stimulation.

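### The only stimulator named gives 50-microsecond constant-voltage pulses, which cannot be the 1 mA, 20-minute direct current that the protocol specifies

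*Combined protocol and SAP*

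**What the plan says.** The device is described once, in CLINICAL TRIAL, section D, under Stimulation: "Electrical stimulation is performed using a constant voltage Cortical Stimulator". Its output is then given as "1000 V/1.5 A) with single square-wave" pulses of 50 µs. The next sentence reads "The adaptor measured resistance prior to stimulation, and divide current during stimulation". The sentence after that sets the dose: "HD tDCS will be delivered in the active condition for 20 minutes of 1 milliamp high definition tDCS per session".

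The dose and modality are stated elsewhere too, always in the same way:

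- Background: the treatment is "transcranial direct-current stimulation (tDCS) on preSMA".
- Preliminary Studies with HD tDCS: the multiple sclerosis study used current "delivered to the preSMA region at 1 mA for 20 min each session, as we propose to use in this project".
- Objective #5: "Half the subjects will first receive HD tDCS at 1 mA for 20 minutes over the preSMA region for 10 daily sessions".
- Aim 1: "Administer 10 20-minute sessions of either 1 mA high definition tDCS or sham to the preSMA region".
- General Experimental Approach, item 5: again 1 mA for 20 minutes in 10 sessions.

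**The concern.** The named device and waveform do not match the named treatment. Direct-current stimulation at 1 mA for 20 minutes is a sustained, regulated current. The device sentence describes brief pulses from a source that fixes voltage and leaves current to follow resistance. The conflict lies inside one paragraph as well as between that paragraph and the rest of the protocol.

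Three things are at stake.

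- **Safety and delivery.** This is the only text that says what equipment passes current through participants' heads. It gives a 1 mA target and a device maximum of 1000 V and 1.5 A. It describes no means of holding the current at 1 mA and no output limit for the session.
- **Sham.** The same section justifies a sham without current on the ground that stimulation at this level cannot be felt. That argument applies only if the active output really is 1 mA.
- **Fidelity.** A monitor could not judge whether a session complied, because a session that follows the device sentence breaks the dose sentence.

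**Working it through.** **Inputs from the documents.** Pulse width 50 µs, maximum output 1000 V and 1.5 A, and electrode resistance below 10 kΩ (section D, Electrodes and Stimulation). Dose 1 mA for 20 minutes = 1,200 s (section D, Objective #5, Aim 1).

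**1. Duration.** 1,200 s / 0.00005 s = 24,000,000. One pulse fills 1/24,000,000 of a session. Continuous current would need 1 / 0.00005 = 20,000 back-to-back pulses per second, which are no longer single pulses.

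**2. Charge.** The specified dose is 0.001 A × 1,200 s = 1.2 C per session.

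| Pulse amplitude | Charge per 50 µs pulse | Pulses needed for 1.2 C | Rate over 1,200 s |
|---|---|---|---|
| 1 mA | 0.05 µC | 24,000,000 | 20,000 per s |
| 1.5 A (device maximum) | 75 µC | 16,000 | 13.3 per s |

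The second row matches the charge only by using pulses that peak at 1.5 A / 0.001 A = 1,500 times the specified current. That is pulsed stimulation, not 1 mA direct current.

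**3. On-time, if the pulses were repeated.** The plan gives no rate, so the rates here are assumptions. At 1 per second: 1,200 × 50 µs = 0.06 s, or 0.005% of the session. At 500 per second: 600,000 × 50 µs = 30 s, or 2.5%.

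**4. Current control.** With a fixed voltage, I = V / R. A setting that gives 1 mA at 10 kΩ is 0.001 × 10,000 = 10 V. At 5 kΩ that voltage gives 2.0 mA, and at 3 kΩ it gives 3.3 mA. The 3 and 5 kΩ values are assumptions, and the path is treated as a single resistor. The plan gives only an upper bound, and gives it for electrode resistance.

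**5. The adaptor.** Dividing a pulse lowers its amplitude and leaves its width at 50 µs. A resistance reading taken before the session is not feedback during the session. Neither function turns pulses into a sustained 1 mA current.

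**6. Side point on electrodes.** An 8 mm disc face has area π × 4² = 50.3 mm², against a stated area of about 85 ± 5 mm². A face plus an edge 1.18 to 1.58 mm high gives 80 to 90 mm². The figure is therefore unclear, but not shown to be wrong.

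**The case against.** The strongest reply is that this is a text error and the treatment design is sound. The dose and modality are the same everywhere, and nearby sentences slip into the past tense, which suggests methods wording carried over from another study. The team also reports having already given ten sessions at 1 mA for 20 minutes, so it probably has suitable equipment. Read as a whole, the paragraph cannot be carried out; it does not order a wrong dose. Staff would have to resolve the conflict before treating anyone, and contact quality and impedance are checked before every session.

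Much of this is fair. A copying error is the likeliest explanation, though the documents do not prove it, and no harmful exposure is shown. The pulse-rate and resistance examples are illustrative; only the duration and charge comparisons rest wholly on stated figures.

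The contradiction remains. No other text names a different stimulator, and impedance checks before a session do not regulate current during it. If the sentence is a copying error, the way to confirm that is to check the equipment record, which is the action requested.

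**Conclusion.** The concern holds. As written, the device and waveform sentence is incompatible with the 1 mA, 20-minute direct current specified in the same paragraph and throughout the protocol. The mismatch is one of kind: a pulse lasts 1/24,000,000 of the session, and the source described fixes voltage where the dose requires a fixed current. This conclusion needs no assumption about pulse rate or resistance and no outside knowledge of the device.

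The figures show the mismatch and do not estimate a planned exposure. Whether any participant would receive a wrong output depends on the equipment actually used, which the documents do not show. Because the sentence is the operative instruction for giving the experimental treatment, it must be corrected before any session. The power calculation is unaffected.

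**What to change.** Before any session:

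- Replace the device and waveform sentence with the stimulator actually used, checked against the equipment record. It should be described as a constant-current direct-current source set to 1 mA for 20 minutes, with a stated output limit, so that it agrees with Objective #5 and Aim 1.
- State what the adaptor does in that set-up.
- As a minor clarification, say which electrode surface the area of about 85 mm² refers to.

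If the record shows that the pulsed device is the one in use, it must be replaced before treatment starts.

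The text change is one or two sentences plus the record check. Dose, sample size, randomisation and analysis stay as they are.

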Treatment of Memory Disorders in Gulf War Illness with high Definition transcranial Direct Cortical Stimulation (GWI HDtDCS)

NCT number: pending

Secondary ID: CDMRP-GW150060

October 6, 2017

BACKGROUND

An estimated 25-32% (175,000 to 210,000) of US military personnel deployed to the theater of operations in Southwest Asia during the 1990-1991 Gulf War (GW) continue to experience a wide array of adverse health problems, including headache, chronic and widespread pain, fatigue, gastrointestinal problems, respiratory problems, sleep problems, and cognitive difficulties, including memory problems.^{1,2,3} Word retrieval deficits, or trouble with finding or "remembering" words one wants to say when speaking, are among the cognitive difficulties reported by deployed GW veterans with possible Gulf War Illness (GWI) and are included in the symptom-report case definitions of GWI.¹⁻⁷ About 24% of deployed GW veterans (GWV), compared to 6-8% of non-deployed controls (NDCs), have reported word retrieval problems, with odds ratio estimates of OR = 2.76-6.39.^{1, 2} Word retrieval is important in verbal fluency (e.g., smoothness or flow with which sounds, syllables, words and phrases are joined together when speaking quickly) and verbal episodic memory (e.g., memory of autobiographical events – times, places, associated emotions, and other contextual who, what, when, where, why knowledge – that can be explicitly *stated*), and may contribute to other reported GWI symptoms, such as deficits in thinking and reasoning.^{5, 7}

The cognitive tests typically used to probe word retrieval via verbal fluency require the production of words that begin with a given letter, that fit a category, or that mediate the association between words. These verbal fluency tasks have been administered to GWV suspected of or identified as having Gulf War Illness (GWI) and have been found useful in identifying those with word retrieval deficits.^{8,9} Retrieval processes also are required for successful retrieval of episodic memories, and those with GWI and memory complaints also show impairments on tests of verbal episodic memory.^{1, 3, 6} Lesions associated with impairments on these word retrieval tasks have also been reported in those with GWI, including the frontal lobes,²²⁻²⁴ temporal lobes,²⁴ the thalamus,²⁵ and the caudate nuclei.²⁶

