Studies reporting symptom prevalence in deployed GWV have led to the proposal of several case definitions.^{1-3, 5, 10-12} The Center for Disease Control and Prevention Chronic Multisymptom Illness case definition requires the presence, for 6 months or longer, of at least one or more symptoms from at least two symptom clusters, which include general fatigue, mood and cognitive abnormalities (including word retrieval/word finding), and musculoskeletal pain.^{1, 3} The Kansas-Steele case definition requires patients to have multiple and/or moderate to severe chronic symptoms in at least three of six defined symptom domains, and qualifying symptoms must have first been a problem during or after the Gulf War and must have persisted over a 6-month period.^{2, 4} Symptoms (including word retrieval/word finding), d) gastrointestinal symptoms, e) respiratory symptoms, and f) skin abnormalities. A third major classification schema, comprising the Haley Syndromes^{5-7, 12} (detailed below), has also been utilized to group patients based on symptom report. None of these classification schemas have clearly delineated specific mechanisms that underlie the observed phenotype.

Our group has published a specific study on verbal fluency (see Preliminary Studies below) in GWV with possible GWI based on the Haley case definitions: impaired cognition (Haley Syndrome 1: HS1), confusion-ataxia (Haley Syndrome 2: HS2), and central pain (Haley Syndrome 3: HS3).⁵⁻⁷ The study showed that on standardized neuropsychological measures of verbal fluency, HS2s and HS3s exhibited impaired verbal fluency compared to case-controls.⁹ Additionally, HS2s showed verbal fluency-related functional and anatomical deficits within the left putamen, in both thalamic hemispheres, and in the right amygdala.

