The efficacy of HD tDCS will be assessed on each outcome. For the cognitive-behavioral measures (i.e., from SORT, COWA, BNT, CVLT, Trails A & B, Color Word Interference, Digits Forward & Backward, Rey-Osterrieth Complex Figures Test, Grooved Pegboard Test, and Beck Depression Inventory), a mixed-model MANOVA initially will be used to test for omnibus group (active vs sham) effects over time (i.e., Group X Time interaction effects). Given a significant multivariate effect, separate univariate mixed-model ANOVAs for each cognitive-behavioral measure will be evaluated for group (active vs sham) effects over time, and significant interaction effects will be followed up by separate pre- versus post-intervention evaluations for each tDCS group. Verbal fluency has been associated with sex, age, and education^{70, 71 but see 72}; thus, these variables will be included in the models. Additionally, potential mediating effects of IQ (based on NAART) and pre-test to post-test change in executive function, simple attention, working memory, processing speed, and depression (measured via Trails A & B, Color Word Interference, Digits Forward & Backward, Rey-Osterrieth Complex Figures Test, Grooved Pegboard Test, and Beck Depression Inventory) will be explored through covariate mediation modeling. For all testing, data will be thresholded for False Discovery Rates (FDR).

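### Tolerability is recorded only after each session and never compared between arms, so a moderate effect of stimulation on fatigue could be masked by the fatigue of Gulf War Illness itself

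*Combined protocol and SAP*

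**What the plan says.** The Stimulation paragraph of CLINICAL TRIAL, part D (HD tDCS Treatment Procedures) sets out the form and its timing: "After each session, patients will be administered a standard post-treatment symptom questionnaire (e.g., assessing for skin irritation, fatigue"). The document describes no earlier administration, either before each session or before the first. The same paragraph has the sham arm wear the cap for the same ten 20-minute sessions without current.

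The BACKGROUND section lists the health problems of this population as including "headache, chronic and widespread pain, fatigue, gastrointestinal problems, respiratory problems, sleep problems". It gives the CDC symptom clusters as those "which include general fatigue, mood and cognitive abnormalities (including word retrieval/word finding), and musculoskeletal pain". CLINICAL TRIAL, part B, Stage 2 classifies participants by the CDC criteria. Skin appears only in the second case definition described, the Kansas one, whose list ends "e) respiratory symptoms, and f) skin abnormalities".

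The STATISTICAL PLAN opens with "The efficacy of HD tDCS will be assessed on each outcome". It then lists the cognitive-behavioural measures, including the depression inventory, and goes on to the EEG analysis. The symptom form is not listed, and no summary of symptoms or adverse events by arm is planned.

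**The concern.** A form completed only after a session records the participant's state at that moment. It does not record what the session did. In people whose illness includes chronic fatigue, many may report fatigue after a session whether or not current was delivered. Two things are then at stake.

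- **Sensitivity between arms.** Background reports raise the rate in both arms and shrink the difference between them, so a moderate effect is harder to see.
- **Attribution within a person.** Without a prior answer, a report of fatigue after, say, the third session cannot be classed as new, worse or unchanged.

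Even the comparison that the design does allow, active against sham on the post-session answers, is not planned. The randomised sessions are the only sham-controlled period, because sham participants go on to active treatment after their follow-up. Pre-session answers not collected in that period cannot be recovered later.

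**Working it through.** The plan states no side-effect rate and no power for tolerability, so there is no figure to reproduce. What follows is an illustration.

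**Inputs from the document:** 80 participants, half to each condition, so 40 per arm; sham participants attend the same capped sessions.

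**Assumptions:** two-sided 5% test; stimulation period causes the symptom in p = 25% of active and 5% of sham participants who would otherwise be free of it; background prevalence b of 30%, 50% or 70% for a common symptom such as fatigue, and 2%, 5% or 10% for a rare local one.

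**Post-session answers only.** Observed rate = b + (1 − b) × p. At b = 0.5, active is 0.5 + 0.5 × 0.25 = 0.625 and sham is 0.5 + 0.5 × 0.05 = 0.525. The true difference of 20 points shrinks to 20 × (1 − b) = 10 points. Power is by exact binomial enumeration of the pooled two-proportion z-test.

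**With a pre-session answer, counting new onset only.** The analysis is limited to those symptom-free beforehand, n = 40 × (1 − b) per arm, at 25% v 5%.

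| Background b | Observed, active v sham | Power, post-only | Symptom-free per arm | Power, new onset |
|---|---|---|---|---|
| 2% | 26.5% v 6.9% | 0.69 | 39 | 0.75 |
| 5% | 28.8% v 9.8% | 0.60 | 38 | 0.74 |
| 10% | 32.5% v 14.5% | 0.48 | 36 | 0.72 |
| 30% | 47.5% v 33.5% | 0.25 | 28 | 0.60 |
| 50% | 62.5% v 52.5% | 0.16 | 20 | 0.44 |
| 70% | 77.5% v 71.5% | 0.09 | 12 | 0.21 |

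If worsening could also be identified perfectly in everyone already symptomatic, all 40 per arm would count at 25% v 5% and power would be 0.76. That is a ceiling, not an expectation.

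**If the form yields a graded score.** The difference detectable with 80% power is (1.96 + 0.84) × √(2/40) × √(1 − r²) SD, where r is the assumed correlation between pre- and post-session scores. Post-only, this is 2.80 × 0.2236 = 0.63 SD. Adjusting for a pre-session score gives 0.54 SD at r = 0.5 and 0.45 SD at r = 0.7. For a true difference of 0.5 SD, power is 0.61 post-only, and 0.73 or 0.88 with adjustment.

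**The case against.** The strongest reply is the randomised sham arm. Background fatigue is balanced in expectation, so a post-only comparison is valid without any pre-session answer. That stands. A reader might infer that a side effect would be lost altogether, or that the trial could give no usable tolerability result, and the documents do not support either. What is lost is precision and attribution in the individual. The reply does not meet the second gap, since the valid comparison is not in the plan.

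Four further points limit the claim.

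- **Skin.** A reader might take both named items as case-defining. Only fatigue falls in the CDC clusters. Skin abnormalities belong to the Kansas definition, and nothing in the document equates them with irritation under an electrode. At backgrounds of 2% to 10% the loss is small to moderate.
- **The form itself.** The two symptoms are examples, and the full form is in a cited source not available here. It may already grade severity or ask about relation to stimulation; the protocol does not say. One cannot assert that every fatigued participant would score positive each time, or that staff could never tell a change.
- **The illustration.** It reduces ten sessions to one yes/no answer per participant. Graded or repeated answers would perform differently. At 70% background, new-onset power is only 0.21, which is low either way.
- **Wider use.** The closing paragraph of OBJECTIVES says that "this treatment can be utilized in any VA medical center or clinic around the nation". A reader might infer a tolerability claim lacking evidence, but the sentence rests on cost, re-use, availability and ease of administration.

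The document also states no tolerability objective or endpoint, and no efficacy conclusion changes. This lowers the priority of the point but does not remove it.

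**Conclusion.** The point holds in a limited form. Two gaps are plain on the page: no answer before the session or at baseline is described, and no active-versus-sham comparison of the form is planned. For fatigue, which overlaps a CDC cluster, a moderate effect could be masked and a single report cannot be classed as new, worse or usual.

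Under the assumed 25% v 5%, restricting to new onset raises power from 0.25 to 0.60, 0.16 to 0.44, or 0.09 to 0.21 at 30%, 50% or 70% background. Every rate and correlation here is assumed, since the document gives none. The direction is firm; the size depends on the true background and on what the form asks. The missing by-arm summary is the simpler gap, because it can be closed with data the plan already collects. Overall this is a cheap improvement, with no bearing on the efficacy analysis.

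**What to change.** 1. In CLINICAL TRIAL, part D, Stimulation: give the same questionnaire before the cap is placed, at minimum before session 1 and preferably before each of the 10 sessions. Add a severity grade per item if the form does not already have one.
2. Define a treatment-emergent symptom as one that is new or worse in grade than the pre-session answer. If only the session 1 answer is collected, use that as the reference.
3. In the STATISTICAL PLAN: add a table of participants with each treatment-emergent symptom during the randomised sessions, active versus sham, with the risk difference and 95% CI.

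The cost is a few more minutes per session, or a single extra form under the minimum option, and one descriptive table. Even if no pre-session form is added, the by-arm table should be, using the post-session answers as collected.
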